#### **7.2.2.5. Analysis of IARs by Onset Intervals**

The IARs will also be analyzed by onset intervals categorized as follows:

- 1 to 3 days, 4 to 7 days, 8 to 14 days, 15 to 28 days, 29 days to  $\leq$  3 months, > 3 months to  $\leq$  6 months, > 6 months to  $\leq$  12 months, > 12 months to  $\leq$  2 years, > 2 years to  $\leq$  3 years, > 3 years to  $\leq$  4 years, and > 4 years.

The event rates and changes in severity over time (over these intervals) will be summarized for each treatment group. This analysis will further describe the clinical characteristics of IARs and help determine whether the IARs disappear over time or appear late.

#### **7.2.2.6. Analysis by Time After Infusion Start**

IARs and anaphylactic reactions will be analyzed by the time after infusion start. Based on protocol descriptions of immediate-type IARs and late-type IARs, the following time after infusion start will be used:

- 0 to  $<$  2 hours, 2 to  $<$  4 hours, 4 to  $<$  6 hours, 6 to  $<$  12 hours, 12 to  $<$  24 hours (1 day), 1 to  $<$  4 days (96 hours).

The event rates and changes in severity over time (over these intervals) will be summarized to help describe the clinical characteristics of IARs and anaphylactic reactions.

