### **11.5. Administration**

#### **11.5.1. Cipaglucosidase Alfa**

The dose of cipaglucosidase alfa, 20 mg/kg, is based on body weight and will be based on the last available body weight value in the IRT system. Weight will be entered into the IRT system at the Baseline Visit, Week 12, Week 26, and every 26 weeks thereafter for calculation of cipaglucosidase alfa dose.

Cipaglucosidase alfa does not contain any preservatives. Vials are single-use only. Reconstituted vials should be retained at the site or the central pharmacy for the home infusion program until the monitor checks accountability.

Cipaglucosidase alfa is to be administered every 2 weeks as an approximate 4-hour IV infusion. Changes in any premedications, dose, rate, or duration of infusion due to safety or tolerability issues will be documented. The total volume of infusion is determined by the subject's body weight. Instructions for preparation for infusion and the volume and rate of infusions will be provided in the pharmacy manual. Reconstitution of cipaglucosidase alfa should be performed by qualified study personnel (eg, pharmacist or pharmacy technician or nurse under physician supervision). Intravenous administration of cipaglucosidase alfa should be performed by qualified study personnel. Subjects should be carefully monitored during and after the first 3 infusions (Section 12.2.2). Any delegation of this responsibility must follow Section 16.3.5. Rate and duration of infusion must be constant for each infusion.

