### 13.1.3. Infusion-associated Reactions

An IAR is defined as a disorder characterized by 1 or more adverse reaction(s) to the infusion of pharmacological or biological substances. These reactions are classified into 2 major subtypes, early and late, according to the time interval between the infusion and the onset of an infusion-related AE.

The reactions are divided into 5 severity grades as follows:

1. Mild (requires observation only); for example, transient flushing or rash
2. Moderate (minimal, usually oral, intervention suffices); for example, urticaria/myalgia/drug fever
3. Severe (vital organ involved yet not in a life-threatening manner; usually requires parenteral medication); for example, bronchospasm/angioedema/hypotension
4. Life threatening (multisystem involvement of vital organs, urgent and critical care required); for example, systemic anaphylactic reaction
5. Death

Early IARs is any symptom or sign occurring during or within 24 hours of completion of the infusion and deemed a drug-related AE by the investigator, unless an alternative obvious explanation exists, eg, mechanical fall. Early IARs commonly involve 1 or more of the following systems: skin (urticaria and erythema), eyes (conjunctivitis), nasopharynx (rhinorrhea, rhinitis), bronchopulmonary tissues (wheezing, bronchospasm), and gastrointestinal tract (diarrhea, vomiting).

Late IAR is any symptom or sign occurring more than 24 hours (usually 1 to 3 days) after completion of the infusion that, in the investigator's opinion, fits the clinical description of a symptom or sign associated with an IAR. The most common symptoms of late IARs are pruritic skin eruptions, fever, malaise, and polyarthralgia.

Note: The list of IAR symptoms provided in [Table 9](#) is not comprehensive. It is meant to serve as a guideline to the investigators to report and manage IAR as AE. [Table 9](#) also provides a guideline for management of IARs and anaphylaxis (see also [Appendix 2](#)). The guideline is intended for sites that do not have such procedures in place. It is at the investigator's discretion to follow the guidelines or implement treatment protocol that their center is accustomed to following.

When an IAR occurs, it is important to report and indicate in the eCRF all AEs that are associated with the IAR. All available details of the events observed with an IAR are necessary to assess the evolution of the AEs after premedication for subsequent infusions.

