### 13.1.4. Relationship to Study Drug

The investigator or a qualified sub-investigator will review each event and assess its relationship to ERT based on available information according to the following guidelines:

- **Definite:** A reaction that follows a distinct temporal relationship from administration of the study drug, that follows a known reaction to the agent or chemical group of the study drug, and that cannot be explained by the subject's clinical state or other factors. By definition, IARs (immediate or late type) are considered definite (see Section 13.1.3).

- **Probable:** A reaction that follows a reasonable temporal sequence from administration of the study drug, that follows a known or expected response pattern to the suspected study drug, and that could not be reasonably explained by the known characteristics of that subject/subject's clinical state.
- **Possible:** A reaction that follows a reasonable temporal sequence from administration of the study drug and that follows a known or expected response pattern to the suspected study drug, but that could readily have been produced by a number of other factors.
- **Unlikely:** A reaction that does not follow a reasonable temporal sequence from administration of the study drug. However, causality from the study drug cannot be ruled out.
- **Unrelated:** A reaction for which sufficient data exist to indicate that the etiology is unrelated to the study drug.

For the purpose of reporting SAEs to regulatory authorities and IRBs/IECs/REBs, any AE assessed by the investigator as definitely, probably, or possibly related to study drug will be considered "related" to study drug (ie, associated with the use of the study drug). Any AE assessed as unlikely or unrelated will be considered "not related" to study drug (ie, not associated with the use of study drug).

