### **15.1. Endpoints**

#### **15.1.1. Safety Endpoints**

The long-term safety profile of cipaglucosidase alfa/miglustat will be characterized using incidence of TEAEs, SAEs, and AEs leading to discontinuation of study drug, frequency and severity of immediate and late IARs, and any abnormalities noted in other safety assessments (eg, clinical laboratory tests, ECGs, vital signs). Immunogenicity to cipaglucosidase alfa will also be described.

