#### **2.3.1. Safety Endpoints**

Safety endpoints to be evaluated include exposure, incidence of treatment-emergent adverse events (TEAEs), serious adverse events (SAEs) including infusion-associated reactions (IARs), AEs leading to discontinuation from the study, TEAEs leading to discontinuation of study drug, TEAEs leading to death, frequency and severity of immediate and late IARs, and abnormalities noted in other safety assessments (eg, clinical laboratory tests, electrocardiograms (ECGs), vital signs).

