#### **7.2.2.2. Specific Summaries of IAR-TEAEs**

To further characterize TEAEs considered by the reporting investigator to be IARs, specific summaries of TEAEs reported as IARs will be provided, where feasible. That is, the number and percentage of subjects who experienced any IAR-TEAEs, IAR-TEAE leading to study drug discontinuation, IAR-TESAE, IAR-TESAE leading to study drug discontinuation, and IAR-TEAE leading to death will be presented by SOC and PT within each SOC, and by treatment group and overall. A subject will be counted only once within the same SOC and within the same PT. A summary of IAR-TEAEs will also be presented by severity (mild, moderate, severe) and by relationship to each treatment component (ciphaglucosidase alfa and miglustat) as well as for the combination treatment (ciphaglucosidase alfa/miglustat).

Listings of treatment-emergent IAR-TEAEs, serious IAR-TEAEs, IAR-TEAEs leading to study drug discontinuation, and IAR-TEAE related deaths will be provided.

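### SAP 7.2.2.6 times IARs from infusion start and stops at 96 h, so its last bin mixes early and late reactions as Protocol 13.1.3 defines them; the immediate/late IAR endpoint is approximated, not missing.

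*SAP*

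**What the plan says.** Protocol 15.1.1 lists "frequency and severity of immediate and late IARs" among the measures that characterise long-term safety, and SAP 2.3.1 carries the same item. Long-term safety and tolerability is the primary objective (Protocol 7.1).

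The split is defined in Protocol 13.1.3, by time from the end of the infusion:

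- "Early IARs is any symptom or sign occurring during or within 24 hours of completion of the infusion", if the investigator judges it drug-related.
- "Late IAR is any symptom or sign occurring more than 24 hours (usually 1 to 3 days) after completion of the infusion", if it fits the clinical picture of an IAR in the investigator's opinion. The bracketed range describes what is usual; it is not a limit.

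SAP 7.2.2.6 says of its bins: "Based on protocol descriptions of immediate-type IARs and late-type IARs, the following time after infusion start will be used". They are 0 to 2, 2 to 4, 4 to 6, 6 to 12 and 12 to 24 hours, then 1 day to under 4 days (96 hours), all counted from infusion start. The section commits to summarising event rates and shifts in severity across these bins.

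On infusion length, Protocol 11.5.1 states: "Cipaglucosidase alfa is to be administered every 2 weeks as an approximate 4-hour IV infusion". Protocol Table 9 describes halving the rate, stopping the infusion, and restarting it later after a reaction.

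**The concern.** The SAP says that its bins rest on the protocol's two IAR types, but it uses a different starting point for the clock. A cut 24 h after start is not the protocol's cut 24 h after completion, and no grouping of the six bins reproduces the protocol split. The bins also stop at 96 h, whereas the protocol's late category is open-ended.

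What is at stake is how precisely a named safety endpoint is reported. A reader of the table could not tell how many IARs in the last bin are early and how many are late under the protocol. The table's rows might also fail to add up to the IAR total, because an onset at 96 h or later has no row.

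**Working it through.** **Inputs**

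- Infusion duration D: about 4 h (Protocol 11.5.1).
- Early/late boundary: 24 h after completion (Protocol 13.1.3).
- Bin cuts: 2, 4, 6, 12, 24 and 96 h after start (SAP 7.2.2.6).
- Rate reduction by half for a mild reaction (Protocol Table 9).

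**1. The SAP's own conversions.** 24 h = 1 day and 4 × 24 = 96 h = 4 days. Both are correct.

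**2. Protocol boundary on the SAP's clock.** Boundary = D + 24. With D = 4 this is 28 h after start. A 24 h cut would match only if the clock began at completion (D = 0).

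**3. Last bin.** Its width is 96 − 24 = 72 h. The part that is early by protocol is (D + 24) − 24 = D hours, a share of D/72. With D = 4: 4/72 = 5.6%.

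**4. Slowed infusion.** Assume the rate is halved t hours after start (t from 0 to 4) and not restored, with no stop and the full dose given. Then D = t + 2(4 − t) = 8 − t, which lies between 4 and 8 h.

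| D | Boundary after start | Early share of last bin | End of last bin, after completion | Usual late range (24 to 72 h after completion), after start |
|---|---|---|---|---|
| 4 h | 28 h | 4/72 = 5.6% | 96 − 4 = 92 h | 28 to 76 h |
| 8 h | 32 h | 8/72 = 11.1% | 96 − 8 = 88 h | 32 to 80 h |

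In both rows the usual late range lies inside the last bin. The percentages are shares of bin width. The documents give no IAR onset counts, so shares of events cannot be stated.

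**5. Bins under 24 h.** Completion cannot precede start. An onset less than 24 h after start is therefore either during the infusion or less than 24 h after its completion, and is early in both cases. This holds for any D, as long as start and completion belong to the same infusion.

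**6. Interrupted infusions.** Table 9 allows a restart 48 h later after a moderate reaction, and after 7 to 14 days for a severe one. Neither document says which start and completion then apply. As an illustration only, assume a 48 h pause, a total running time of 4 h, and one infusion counted from its first start. Completion is then at 4 + 48 = 52 h and the boundary at 52 + 24 = 76 h, so 52/72 = 72% of the last bin is early. The usual late range becomes 76 to 124 h (52 + 72 = 124) and runs past the end of the table. If the restart counts as a new infusion with its own clock, the boundary is again 24 h plus that session's length. The result depends on a rule that is not written down.

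**7. Other planned IAR outputs.** SAP 7.2.2.1 to 7.2.2.5 cover an overview, system organ class and preferred term, severity, relationship, infusions with IARs, counts per subject, time to first IAR, and onset intervals. The onset intervals run beyond 4 years, so with dosing every 2 weeks they are not time since the triggering infusion. None of these outputs classifies IARs as early or late.

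**The case against.** The strongest reply is that saying bins are based on the protocol descriptions does not claim to reproduce them. Section 7.2.2.6 aims to describe clinical characteristics and plans both frequency and severity over its bins. For a single continuous infusion five of the six bins are purely early, and the sixth holds the whole usual late range. The 8-hour case needs the rate halved from the outset and never restored, and Table 9 is a guideline used at the investigator's discretion. The reaction that prompts slowing begins during the infusion, so it falls in an unaffected bin. All of this stands, and it limits the point to one mixed bin and a truncated range.

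A reader might infer more than the documents support:

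- *That the endpoint has no planned analysis, or that severity is never shown by timing.* Section 7.2.2.6 plans both, on an approximate split.
- *That IARs at 96 h or later vanish from the report.* They remain in the other IAR summaries and listings; only this table lacks a row, and nothing shows that the row would be populated.
- *That 5.6% or 11.1% of IARs are misplaced.* Those are fractions of clock time.
- *That immediate and early are two different categories.* Protocol 13.1.4 says "By definition, IARs (immediate or late type) are considered definite" and refers to 13.1.3, so the same split is meant.

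The reply does not remove the mismatch. A stated protocol basis with a different clock origin invites readers to take the 24 h cut as the protocol boundary, and no other output supplies that boundary.

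**Conclusion.** The mismatch is real and minor. For uninterrupted 4-hour infusions, 4 of the 72 hours in the last bin are early by protocol. With the rate halved under the assumptions above, the figure is at most 8 of 72. The last bin reaches 88 to 92 h after completion, beyond the usual late range but short of the protocol's open-ended category. The endpoint is approximated, and the number of affected events is probably small, though the documents do not allow a count.

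Interrupted and restarted infusions are the one situation in which the gap could be wide, and its size depends on a convention that neither document states. The analyses are descriptive with no formal tests, so nothing inferential is affected.

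**What to change.** 1. Keep the start-based bins in SAP 7.2.2.6, add an open-ended bin of 96 h or more, and state that the bins are not the protocol's early/late classification.
2. Where infusion stop time or duration is in the database, add one table of early (immediate) versus late IARs timed from completion under Protocol 13.1.3: 24 h or less is early, more than 24 h is late. Show the number of IARs and the number and percentage of subjects in the OLE safety population, by severity, by the two treatment groups and overall. Name the severity scale, because SAP 7.2.2.2 uses three levels while Protocol 13.1.3 lists five IAR grades.
3. State which start and completion times the analysis uses for interrupted or restarted infusions. This is an analysis convention only and changes no clinical rule.
4. Under a convention that takes both times from the same infusion, completion time is needed only for onsets 24 h or more after start. Where it is needed but missing, show those IARs in a not-classifiable row.

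The cost is some SAP wording, one bin and, if the data exist, one table. Check availability first. Event start time is recorded (Protocol 13.2), but Protocol 12.2.2 promises eCRF entry only for changes in infusion duration, and Table 9's instruction to record times and rates does not name the eCRF. With data cut off at 31 December 2024, stop times that were never collected may not be recoverable. Items 1 and 3 can be done regardless.

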### **7.3. Clinical Safety Laboratory Data**

Laboratory data will be presented using the Système International (SI) unit. Descriptive statistics (n, mean, SD, median, Q1, Q3, minimum, and maximum) will be presented for the absolute visit values, change from baseline, and percent change from baseline to post-baseline visits by treatment group and overall, and by visit, starting at the Baseline visit. Summaries will be presented by the specific lab parameters within the domains of clinical chemistry, hematology, and urinalysis.

Line plots of mean  $\pm$  SE of the change from baseline and percent change from baseline over time will be provided for alanine aminotransferase (ALT) and aspartate aminotransferase (AST) by treatment group and overall. Similar line plots will also be provided by prior ERT status.

Additionally, a summary of the number and percentage of subjects with treatment-emergent or newly-occurring laboratory values that meet pre-defined limits of change (PDLC) at any post-baseline visit will be presented by treatment group and overall. The PDLC criteria are provided in [Table 4](#). If a subject has even 1 post-baseline value that meets the PDLC criteria for any particular lab parameter, then all values of that parameter for that subject will be listed.

**Table 4: Pre-defined Limits of Change Criteria for Clinical Safety Laboratory Data**

| Laboratory Test                 | Parameter for ANY Value and LAST Value  |
|---------------------------------|---|
| Chemistry                |   |
| Albumin                         | Composite: < LLN and > 25% decrease from BL   |
| Bilirubin                       | Composite: > ULN and > 25% increase from BL   |
|                                 | Absolute Value: > 2X ULN  |
| Bicarbonate                     | Absolute Value: < 16 mEq/L  |
| Calcium                         | Composite: > ULN and > 10% increase from BL   |
| Phosphorus                      | Composite: < LLN and > 25% decrease from BL   |
|                                 | Composite: > ULN and > 25% increase from BL   |
| Potassium                       | Composite: < LLN and > 15% decrease from BL   |
|                                 | Composite: > ULN and > 15% increase from BL   |
| Sodium                          | Composite: < LLN and decrease > 5 mEq/L or more from BL   |
|                                 | Composite: > ULN and increase > 5 mEq/L or more from BL   |
| Uric Acid                       | Male: absolute value $\geq$ 624.6 $\mu$ M   |
|                                 | Female: absolute value $\geq$ 505.6 $\mu$ M   |
|                                 | Composite: < LLN and > 25% decrease from BL   |
|                                 | Composite: > ULN and > 25% increase from BL   |
| ALT                             | Absolute Value: > 3X ULN  |
|                                 | Absolute Value: > 5X ULN  |
|                                 | Absolute Value: > 8X ULN  |
| AST                             | Absolute Value: > 3X ULN  |
|                                 | Absolute Value: > 5X ULN  |
|                                 | Absolute Value: > 8X ULN  |
| ALT > 3X ULN and Tbili > 2X ULN | Composite: ALT > 3X ULN and Tbili > 2X ULN (with the Tbili elevation > 2X ULN within 30 days of the ALT elevation > 3X ULN) |
| AST > 3X ULN and Tbili > 2X ULN | Composite: AST > 3X ULN and Tbili > 2X ULN (with the Tbili elevation > 2X ULN within 30 days of the AST elevation > 3X ULN) |
| CK                              | Absolute CK $\geq$ 2X ULN or 2X baseline value  |

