#### **15.3.4.4. Safety Analyses**

Safety analyses will be based on the safety population (for ATB200-03 and ATB200-07 integrated data) as well as the open-label extension safety population (for ATB200-07 stand-alone data).

Safety data will be summarized using descriptive statistics for continuous data and using counts and percentages for categorical data, as described in Section [15.3.3.6](#).

Exposure to study medication will be calculated in weeks and analyzed as continuous variables using descriptive statistics. In addition, the duration of exposure will be categorized and a frequency distribution of the categories (each summarized by count and percentage) will be presented.

An overall summary of incidence of AEs (which includes the total number of TEAEs, total number of serious TEAEs as well as the total number of subjects) will be presented. The number and percentage of subjects who experienced nonserious TEAEs as well as serious TEAEs will be summarized by preferred term within system organ class. The summary of nonserious and serious TEAEs will also be presented by intensity (mild, moderate, severe), as well as by relationship to study medication. In addition, the number of AEs (as opposed to the number and percentage of subjects) will be presented.

Serious adverse events, including deaths, will be summarized and listed. Separate listings of death, SAEs (treatment-emergent and nontreatment-emergent), and discontinuations due to AEs will be provided.

Summaries and listings will also be provided for deaths, SAEs, and AEs leading to discontinuation and infusion-associated reactions. Adverse events will be coded using Medical Dictionary for Regulatory Activities version 18 or higher.

Clinical laboratory results, ECG parameters, and vital signs will be summarized using descriptive statistics (number, mean, median, standard deviation, minimum, and maximum) by treatment group and visit for actual values and changes from baseline. The proportion of subjects with abnormalities will be provided for clinical laboratory results, ECGs, and vital signs. Shift tables will also be provided for clinical laboratory results.

Prior and concomitant medications and nondrug therapies will be summarized by treatment group. Concomitant medications terms will be coded using the World Health Organization Drug Dictionary (September 2013 DDE).

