### **APPENDIX 3. POTENTIALLY CLINICALLY SIGNIFICANT GUIDELINES**

Criteria for identifying abnormalities as potentially clinically significant are based on the Guidelines for the Division of Neuropharmacological Drug Products, US Food and Drug Administration (revised on 2 April 1987). The laboratory values identified below are not inclusive of all the safety laboratory analytes that will be assessed during this clinical trial. Safety laboratory analytes that are known to be elevated in some adults with Pompe disease (eg, aspartate aminotransferase, alanine aminotransferase, lactate dehydrogenase) and safety laboratory analytes which are not listed below will be reviewed to determine if they are to be noted as potentially clinically significant based on the magnitude of the out of range value as compared with the normal range and the subject's baseline value, and whether the out of range value is coded as clinically significant by the principal investigator.

Laboratory Values		
Variable	Criterion Values	
	Standard Units	SI Units
Chemistry		
SGOT (AST)	$\geq 3 \times$ Upper Limit Normal	
SGPT (ALT)	$\geq 3 \times$ Upper Limit Normal	
Alkaline Phosphatase	$\geq 3 \times$ Upper Limit Normal	
LDH	$\geq 3 \times$ Upper Limit Normal	
BUN	$\geq 30$ mg/dL	$\geq 10.7$ $\mu$ M
Creatinine	$\geq 2.0$ mg/dL	$\geq 176.8$ $\mu$ M
Uric Acid	Male Female	$\geq 10.5$ mg/dL $\geq 8.5$ mg/dL
Bilirubin (Total)		$\geq 34.2$ $\mu$ M
Hematology		
Hematocrit	Male Female	$\leq 37\%$ $\leq 32\%$
Hemoglobin	Male Female	$\leq 11.5$ g/dL $\leq 9.5$ g/dL
Platelets		$\leq 75,000/\text{mm}^3$ or $\geq 700,000/\text{mm}^3$
Leukocytes		$\leq 2,800/\text{mm}^3$ or $\geq 16,000/\text{mm}^3$
Eosinophils		$\geq 10\%$
Neutrophils		$\leq 15\%$
Urinalysis		
Protein	Increase of $\geq 2$ units	
Glucose	Increase of $\geq 2$ units	
Casts	Increase of $\geq 2$ units	

Abbreviations: BUN = blood urea nitrogen; LDH = lactate dehydrogenase; SGOT (AST) = serum glutamic oxaloacetic transaminase (aspartate aminotransferase); SGPT (ALT) = serum glutamic pyruvic transaminase (alanine aminotransferase)

Vital Sign Values			
Variable	Criteria		Change Relative to Baseline
Heart Rate	$\geq 120$ bpm	and an	increase of $\geq 15$ bpm
	$\leq 50$ bpm	and a	decrease of $\geq 15$ bpm
Systolic Blood Pressure	$\geq 180$ mmHg	and an	increase of $\geq 20$ mmHg
	$\leq 90$ mmHg	and a	decrease of $\geq 20$ mmHg

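### The SAP's ALT/AST abnormality count uses multiples of ULN only, with no baseline-relative limit, and the protocol's laboratory shift tables are left out without a reason

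*SAP*

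**What the plan says.** SAP Table 4 gives ALT and AST three limits each. The lowest is "Absolute Value: > 3X ULN"; the others are 5X and 8X ULN. The liver composites are built the same way, for example "Composite: ALT > 3X ULN and Tbili > 2X ULN". Most other chemistry rows in the table include a change from baseline, and the row for CK, also a muscle enzyme, reads "Absolute CK $\geq$ 2X ULN or 2X baseline value".

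SAP 7.3 counts "subjects with treatment-emergent or newly-occurring laboratory values that meet pre-defined limits of change" at any post-baseline visit. It does not define treatment-emergent or newly-occurring for laboratory values. The accompanying listing has a looser trigger: "If a subject has even 1 post-baseline value that meets the PDLC criteria for any particular lab parameter", all of that subject's values for the parameter are listed. SAP 7.3 also plans summaries of "absolute visit values, change from baseline, and percent change from baseline to post-baseline visits", and line plots of change and percent change for ALT and AST.

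Protocol Appendix 3 names AST, ALT and LDH as examples of analytes known to be raised in some adults with Pompe disease. It says they will be reviewed on the "magnitude of the out of range value as compared with the normal range" and with the subject's baseline value, together with the investigator's own coding. Protocol 15.3.4.4 adds: "Shift tables will also be provided for clinical laboratory results". SAP 7.3 contains no shift table and does not say why.

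**The concern.** Safety is the primary objective, and the count of subjects meeting a limit is the subject-level laboratory result that a reader of the report is likely to look at first. ALT and AST in this disease may start above normal because they come from muscle. A limit fixed in ULN multiples then asks a different question of each subject. Near 3X ULN, ordinary variation is enough to cross it; at 1X ULN, the value has to triple. The protocol recognises this in Appendix 3 and the SAP recognises it for CK, but the ALT and AST rows do not. A shift table with suitable categories would show each subject's starting point next to the worst value, and that display has been dropped.

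**Working it through.** The plan states no figure to reproduce on this point. There are two checks: one on the thresholds alone, and one that needs assumptions.

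**1. Thresholds alone (no assumption).** Inputs are the limits 3, 5 and 8 x ULN from SAP Table 4. The fold rise needed to reach the next limit is the next limit divided by baseline.

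| Baseline (x ULN) | Next limit | Fold rise needed |
|---|---|---|
| 1.0 | 3 | 3.0 |
| 1.5 | 3 | 2.0 |
| 2.0 | 3 | 1.5 |
| 2.9 | 3 | 1.03 |
| 3.1 | 5 | 1.61 |
| 5.1 | 8 | 1.57 |
| above 8 | none | no further limit |

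So a rise of about 3.4% (3.0/2.9 = 1.034) from 2.9X adds a subject to the count, while a rise from 1X to 2.9X does not.

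**2. A stable subject (assumptions needed).** Assume lognormal values around a constant median m (in x ULN), independent between visits, with within-subject CV as given. Use 12 post-baseline tests, Weeks 2 to 208 in SAP Table 2. Read newly-occurring as baseline at or below 3X.

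- s = sqrt(ln(1 + CV²))
- p = P(Z > ln(3/m)/s), the chance that one test exceeds 3X
- P(flag, given baseline at or below 3X) = 1 - (1 - p)^12

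For m = 2.5 and CV 20%: s = 0.198, ln(1.2)/0.198 = 0.921, p = 0.179, and 1 - 0.821^12 = 0.91. Multiplying by the chance that baseline itself is at or below 3X (0.821) gives 74% of all such subjects.

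| True level | CV 10% | CV 15% | CV 20% |
|---|---|---|---|
| 2.5X ULN | 34% | 76% | 91% |
| 2.0X ULN | below 0.1% | 4% | 22% |
| 1.5X ULN | about 0 | about 0 | 0.3% |

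**3. Effect of a baseline condition.** Require both more than 3X ULN and at least 2X baseline, borrowing the multiple from the CK row. For the stable subject at 2.5X and CV 20%, the share of all such subjects flagged over 12 tests falls from 74% to 5% (simulated). At CV 30% and 13 tests it falls from 72% to 27%, so the gain is smaller when variation is large.

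**4. BUN unit (separate).** The Appendix 3 limit of 30 mg/dL urea nitrogen converts as 30 x 10 / 28.014 = 10.7 mmol/L. The SI column, as extracted, shows 10.7 µM, which differs by a factor of 1000.

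**The case against.** The case for leaving the plan alone has five parts.

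- **Appendix 3 is not a tabulation rule.** Its own table lists AST and ALT at 3 x ULN or more with no baseline term, and protocol 12.3.11.1 cites the appendix for the investigator's significance call. This stands: the two documents are unreconciled, but the SAP breaches nothing.
- **The SAP may drop the shift tables.** SAP Section 1 says that it supersedes the protocol's analyses. This also stands; what is missing is a reason.
- **Stable subjects above 3X are not counted.** On the ordinary reading of newly-occurring, a subject who starts above 3X and stays there appears in the listing but not in the count. That is a fair reading, but the SAP does not write it down. The figures above already apply it, so the problem left is with subjects just below the limit.
- **Baseline-relative analysis is already planned.** By-visit change and percent change with quartiles and maximum, ALT/AST plots, and full listings all remain. CK has its own change plots (SAP 6.2). This stands for the analysis as a whole, but none of these displays counts subjects with a marked individual rise.
- **The high percentages depend on a true level near 3X.** Correct, as the 2.0X and 1.5X rows show.

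A reader might go further and infer that true rises between limits go unseen, for example from 3.2X to 4.9X ULN. The check does not support this. With the same noise at CV 20%, 98.7% of such subjects record a new value above 5X over 12 tests. Nor would a 2X-baseline row be the remedy there, since 4.9/3.2 = 1.53. A reader might also infer that most of the reported abnormalities will be baseline artefacts; the documents contain no data that could show this.

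**Conclusion.** The point holds as a weakness in one safety display. The ALT/AST count has no baseline-relative limit, its newly-occurring restriction is undefined for laboratory data, and the planned shift tables are absent without explanation. That the count depends on baseline position follows from the thresholds alone. The size of any false flagging rests on assumed CVs and true levels: large for stable subjects near 2.5X ULN (34-91% at CV 10-20%), modest at 2.0X (4-22% at CV 15-20%) and negligible at 1.5X. Without a baseline distribution or a CV in the documents, the number of subjects affected cannot be computed. It is worth correcting because safety is the primary objective and the correction is cheap.

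The BUN unit is a side matter. SAP Table 4 has no BUN row, so no planned count changes, and the extracted table is visibly broken, so the symbol may be an extraction error.

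**What to change.** In SAP 7.3 and Table 4:

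1. Keep the ULN rows and composites as they are.
2. Define newly-occurring for laboratory data, for example: the baseline value did not meet the same limit.
3. Report the ALT and AST rows split by baseline at or below ULN and above ULN.
4. For subjects with baseline above ULN, add an ALT/AST row such as at least 2X baseline and more than 3X ULN. This mainly removes false flags; it is not meant to catch smaller rises.
5. Restore the laboratory shift tables, from baseline to worst and to last post-baseline category. For ALT and AST use at or below ULN, above ULN to 3X, above 3X to 5X, above 5X to 8X, and above 8X. The categories matter: with low/normal/high only, a move from 2.5X to 3.1X would show as high to high. With these, a rise from 1X to 2.9X becomes visible as a change of category.

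Add a sentence reconciling the SAP limits with Appendix 3. Separately, check the Appendix 3 BUN SI unit against the source document and reconcile it with the mg/dL limit.

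The cost is SAP wording, standard shift-table programs and a few more table rows. No new data are needed.
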